2.2. Exploratory Objectives

The exploratory objectives are:

- Assess the number of days requiring ICU care relative to treatment group.
- Assess the number of days of NIV, high-flow O2 or mechanical ventilation relative to treatment group.
- Assess incidence of WHO COVID-19 Classification levels relative to baseline serum IL-6 level.
- Assess incidence of WHO COVID-19 Classification levels relative to baseline serum ferritin level.
- Assess incidence of WHO COVID-19 Classification levels relative to baseline CRP
- Assess trough level of GLS-1027 relative to serum creatinine.
- Assess the maximal level of Positive End-Expiratory Pressure (PEEP) for subjects who are intubated relative to treatment group.
- Assess the number of days of PEEP > 5 cm H2O for subjects who are intubated relative to treatment group.
- Assess change in WHO COVID-19 Classification level at Day 28 from enrollment, relative to group.
- Assess SARS-CoV-2 IgM antibody responses relative to treatment group.

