8.4. Analysis of the Exploratory Efficacy Endpoints

PEEP values during intubation will be plotted separately by treatment over time. Assessment of WHO COVID-19 Classification at 28 day relative to treatment group is discussed in Sections 8.1 and 8.2. Shift tables for worst (most extreme) values of serum IL-6 level, serum ferritin level, and CRP relative to baseline will be presented for each WHO COVID-19 Classification level.

The number of days in ICU, requiring mechanical ventilation and of PEEP > 5 cm H₂O will be summarized by treatment using descriptive statistics (sample size, mean, median, SD, minimum, maximum).

The number and percentage of subjects will be summarized by treatment according to their SARS-CoV-2 IgM antibody response. The above exploratory endpoint analyses will be presented for the PP population and individual results will be listed by treatment and study day. No formal statistical analysis is planned.

CONFIDENTIAL Page 12 03DEC2021

The relationship of trough level of GLS-1027 to serum creatinine relative to treatment group will be examined on an adhoc basis and is outside the scope of this document.

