	GLS-1027	GLS-1027	Placebo
	120 mg	360 mg	(N=XX)
	(N=XX)	(N=XX)	· · ·
umber of Days in Hospital			
n	X	x	x
Mean (SD)	xx.xx (xx.xxx)	xx.xx (xx.xxx)	xx.xx (xx.xxx)
Median	x.xx	x.xx	x.xx
Min, Max	xx.x, xx.x	xx.x, xx.x	xx.x, xx.x

Reference: Listing xxxxx

Programming note: Repeat for Table 14.2.2.8.2 Summary of the Number of Days in Hospital (PP Population).

Table 14.2.3.1

Cumulative Incidence of SARS-CoV-2 IgM Antibody Response by Study Day

(PP Population)

Study Day	GLS-1027	GLS-1027	Placebo
Responded	120 mg	120 mg	(N=XX)
	(N=XX)	(N=XX)	`n(%)´
	,	· · · · · · · · · · · · · · · · · · ·	
Day 1			
n	X	X	X
Yes	x (xx.x%)	x (xx.x%)	x (xx.x%)
No	x (xx.x%)	x (xx.x%)	x (xx.x%)
Day 2			
n	X	x	Х
Yes	x (xx.x%)	x (xx.x%)	x (xx.x%)
No	x (xx.x%)	x (xx.x%)	x (xx.x%)
Day 3			
n	X	X	X
Yes	x (xx.x%)	x (xx.x%)	x (xx.x%)
No	x (xx.x%)	x (xx.x%)	x (xx.x%)
Day 4			
n	X	X	X
Yes	x (xx.x%)	x (xx.x%)	x (xx.x%)
No	x (xx.x%)	x (xx.x%)	x (xx.x%)
	(,	~ ()	. (,
••			

The incidence of antibody response is summarized based on results obtained at or prior to the study day. Reference: Listing 16.2.6.3

Table 14.2.4.1
WHO COVID-19 Classification Levels Relative to Baseline Serum Ferritin Level
(PP Population)

			GL	S-1027			GLS-1027								
				L20 mg			360 mg			Placebo			0verall		
WHO Classification	(N=XX)						(N=XX)			(N=XX)		(N=XX)			
Level	Serum Ferritin [1]	Post-Baseline					Post-Baseline			Post-Baseline			Post-Baseline		
	Baseline	Low	N	lormal	High	Low	Normal	High	Low	Normal	High	Low	Normal	High	
5	n	х		х	x	x	х	х	х	х	x	x	х	х	
	Low					XX	XX	XX	XX	XX	XX	XX	XX	XX	
		xx (xx	.x) xx	(xx.x) xx	(xx.x)	(xx.x)	(xx.x)	(xx.x)	(xx.x)	(xx.x)	(xx.x)	(xx.x)	(xx.x)	(xx.)	
	Normal					XX	XX	XX	XX	XX	XX	XX	XX	XX	
		xx (xx	.x) xx	(xx.x) xx	(xx.x)	(xx.x)	(xx.x)	(xx.x)	(xx.x)	(xx.x)	(xx.x)	(xx.x)	(xx.x)	(xx.	
	High					XX	XX	XX	XX	XX	XX	XX	XX	XX	
		xx (xx	.x) xx	(xx.x) xx	(xx.x)	(xx.x)	(xx.x)	(xx.x)	(xx.x)	(xx.x)	(xx.x)	(xx.x)	(xx.x)	(xx.	
6	n	х		х	x	x	х	х	х	х	x	x	х	х	
	Low					XX	XX	XX	XX	XX	XX	XX	XX	XX	
		xx (xx	.x) xx	(xx.x) xx	(xx.x)	(xx.x)	(xx.x)	(xx.x)	(xx.x)	(xx.x)	(xx.x)	(xx.x)	(xx.x)	(xx.	
	Normal					XX	XX	XX	XX	XX	XX	XX	XX	XX	
		xx (xx	.x) xx	(xx.x) xx	(xx.x)	(xx.x)	(xx.x)	(xx.x)	(xx.x)	(xx.x)	(xx.x)	(xx.x)	(xx.x)	(xx.	
	High					XX	XX	XX	XX	XX	XX	XX	XX	XX	
		xx (xx	.x) xx	(xx.x) xx	(xx.x)	(xx.x)	(xx.x)	(xx.x)	(xx.x)	(xx.x)	(xx.x)	(xx.x)	(xx.x)	(xx.	
7	n	х		х	x	x	x	х	х	х	x	x	х	х	
	Low					XX	XX	XX	XX	XX	XX	XX	xx	XX	

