Subject ID	Study Day	CPAP Prescribed	Date of CPAP U	seMaximal Daily Level of End Expiratory Pressure Delivered by CPAP (cm)	Was ECMO prescribed?	Date of ECMO prescription	Was patient admitted to I	Date of ICU CU?Admission
xxxxx	Day 1	Yes/No	yyyy-mm-dd	xxx.xx	Yes/No	yyyy-mm-dd	Yes/No	yyyy-mm-dd
	Day 2	Yes/No	yyyy-mm-dd	xxx.xx	Yes/No	yyyy-mm-dd	Yes/No	yyyy-mm-dd
xxxxx	Day 1	Yes/No	yyyy-mm-dd	xxx.xx	Yes/No	yyyy-mm-dd	Yes/No	yyyy-mm-dd
	Day 2	Yes/No	yyyy-mm-dd	xxx.xx	Yes/No	yyyy-mm-dd	Yes/No	yyyy-mm-dd
xxxxx	Day 1	Yes/No	yyyy-mm-dd	xxx.xx	Yes/No	yyyy-mm-dd	Yes/No	yyyy-mm-dd
	Day 2	Yes/No	yyyy-mm-dd	xxx.xx	Yes/No	yyyy-mm-dd	Yes/No	yyyy-mm-dd

Listing 16.2.6.5
SARS-COV-2 IgM Antibody Titer and Response

Treatment: GLS-1027 120 mg

Subject ID	Study Day	Date of Assessment	Titer
xxxxxx	Day 1	yyyy-mm-dd	xxx
	Day 7	yyyy-mm-dd	xxx
xxxxxx	Day 1	yyyy-mm-dd	xxx
	Day 7	yyyy-mm-dd	xxx
xxxxxx	Day 1	yyyy-mm-dd	xxx
	Day 7	yyyy-mm-dd	xxx
Source: \\xx\xxx\xxx\x	xxx/xxxxx/xxxxxxxxxxx/xxxx/xxx	x.sas date time	

Protocol: GLS27-005

Listing 16.2.7.1 Adverse Events

Treatment: GLS-1027 120 mg

Subject ID	System Organ Class/ Preferred Term/ Verbatim Term	Start Date (Study Day)	End Date (Study Day)	Severity	Relationship	Action Taken	Serious	Outcome	Study Discontinuation	Treatment Required
xxxxx	xxxxxxxxxxxxx/ xxxxxxxxxxxxxx/ xxxxxxxx	yyyy-mm-dd (xx)	yyyy-mm-dd (xx)	Grade x	xxxxxxxx	xxxxxxxxx	Yes/No	xxxxxxxxx	Yes/No	Yes/No
xxxxx	xxxxxxxxxxxxx/ xxxxxxxxxxxxxxxxxxxxxxx	yyyy-mm-dd (xx)	yyyy-mm-dd (xx)	Grade x	xxxxxxxxx	xxxxxxxxx	Yes/No	xxxxxxxxx	Yes/No	Yes/No
xxxxx	xxxxxxxxxxxxx/ xxxxxxxxxxxxxx/ xxxxxxxx	yyyy-mm-dd (xx)	yyyy-mm-dd (xx)	Grade x	xxxxxxxxx	xxxxxxxxx	Yes/No	xxxxxxxxx	Yes/No	Yes/No

date time

Programming Note: Repeat for each treatment group. Sort by Treatment, Subject ID, AE start date and end date.

Repeat Layout of Listing 16.2.7.1 for:

Listing 16.2.7.3 Adverse Events Leading to Study Discontinuation

Protocol: GLS27-005

Listing 16.2.7.2 Serious Adverse Events

Treatment: GLS-1027 120 mg

Subject ID	System Organ Class/ Preferred Term/ Verbatim Term		End Date (Study Day)	Severity	Relationship	Action Taken	SAE Criteria	Outcome	Study Discontinuation	Treatment Required
xxxxx	xxxxxxxxxxxxx/ xxxxxxxxxxxxxxxxxxxxxxx	yyyy-mm-dd (xx)	yyyy-mm-dd (xx)	Grade x	xxxxxxxx	xxxxxxxxx	xxxxxxxxx	xxxxxxxx	Yes/No	Yes/No
xxxxx	xxxxxxxxxxxxx/ xxxxxxxxxxxxxxxxxxxxxxx	yyyy-mm-dd (xx)	yyyy-mm-dd (xx)	Grade x	xxxxxxxx	xxxxxxxxx	xxxxxxxxx	xxxxxxxxx	Yes/No	Yes/No

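### IgM titre is recorded for each subject, but the only summary by arm is a cumulative Yes/No with no stated cut, which loses much of the information on this exploratory objective

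*SAP*

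**What the plan says.** SAP 2.2 lists as an exploratory objective: "Assess SARS-CoV-2 IgM antibody responses relative to treatment group". It gives no direction, hypothesis or effect size.

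SAP 8.4 sets the summary: "The number and percentage of subjects will be summarized by treatment according to their SARS-CoV-2 IgM antibody response". It uses the per-protocol population, adds that "individual results will be listed by treatment and study day", and closes with "No formal statistical analysis is planned".

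SAP Appendix C, Table 14.2.3.1, is titled "Cumulative Incidence of SARS-CoV-2 IgM Antibody Response by Study Day". Its rows are n, Yes and No for each day, and its footnote reads: "The incidence of antibody response is summarized based on results obtained at or prior to the study day".

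SAP Appendix E, Listing 16.2.6.5, is titled "SARS-COV-2 IgM Antibody Titer and Response". Its layout has a titre column by subject and study day and no response column. The days shown are 1 and 7. SAP Table 1 schedules serum on Days 1, 7 and 14.

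**The concern.** Three features act together.

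- **A numeric result is reduced to two categories.** SAP 8.4 gives ICU days, ventilation days and days of raised PEEP a mean, median and SD. IgM titre, also numeric, gets no summary by arm.
- **The cut is not stated.** The SAP text gives no threshold, fold-rise or seroconversion rule. The programmer cannot derive the Yes row from the plan, and nothing fixes the rule before unblinding.
- **The count is cumulative.** A Day 1 positive remains a Yes throughout and the responder share can only rise. The table therefore drifts toward saturation, which is where a Yes/No split loses most.

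At stake is whether the table can inform its own objective. If titres differed by arm but most subjects were above the cut, the arms would look alike.

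**Working it through.** **Inputs from the documents.** 44 per arm (SAP 4); titre recorded per subject and day (Listing 16.2.6.5); cumulative Yes/No (Table 14.2.3.1). No power, alpha or effect is stated for IgM, so there is no figure of the plan's to reproduce.

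**Assumptions, not in the documents.** Log titre is normal with equal SD in the arms; the shift is d = 0.5 SD; placebo responder share p0 is 50% to 95%; two-sided 0.05; all 44 per arm have a sample. The last is generous, because the per-protocol set will be smaller.

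**Step 1: information kept by a Yes/No split.** For a normal variable cut so that a share p responds, the share kept is φ(z)²/[p(1−p)], with z = Φ⁻¹(p).

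- p = 0.50: 0.399²/0.25 = 64%
- p = 0.80: 0.280²/0.16 = 49%
- p = 0.90: 0.1755²/0.09 = 34%
- p = 0.95: 0.1031²/0.0475 = 22%

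The loss passes one half only when the share is above about 79% or below about 21%.

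**Step 2: power on Yes/No.** The active share is p1 = Φ(Φ⁻¹(p0) − 0.5). Fisher power is by exact enumeration; the z test has no continuity correction.

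| Placebo positive | Active positive | Fisher | z test |
|---|---|---|---|
| 50% | 30.9% | 36.2% | 44.7% |
| 80% | 63.4% | 32.0% | 40.8% |
| 90% | 78.3% | 22.9% | 32.3% |
| 95% | 87.4% | 12.6% | 24.0% |

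**Step 3: power on log titre.**

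- Unadjusted: noncentrality 0.5 × √(44/2) = 2.345 on 86 df gives 64.0%.
- Adjusted for Day 1 with correlation 0.5: effective shift 0.5/√(1 − 0.25) = 0.577, noncentrality 2.708, power 76.4%.

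**Step 4: values below the assay limit.** Step 3 treats every titre as observed. A simulation took the cut as the assay limit, set lower values to half the limit, and assumed an SD of 1.0 to 1.5 on the natural log scale. With 50% of placebo positive, unadjusted power falls to about 51%. At 80% positive or more it stays close to 64%.

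**Step 5: like with like.**

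- At 50% positive: 51% on titre against 36% on Yes/No, a gap of 15 points.
- At 95% positive: about 64% against 13%, a gap of 51 points.
- Against the uncensored 64.0%, Yes/No keeps 36.2/64.0 = 57% of the power at 50% positive, 32.0/64.0 = 50% at 80%, and 12.6/64.0 = 20% at 95%.

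With 30 per arm, Fisher gives 24%, 21%, 13% and 5% across the same shares, against 48% for uncensored log titre and 59% with Day 1 adjustment.

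**The case against.** The strongest reply is that there is no test whose power could be lost. SAP 8.4 plans no formal analysis, IgM is one of many exploratory items, and Fisher's test belongs to the primary endpoint. That stands: the powers above only measure how well each display could separate the arms. Some of the gap is also Fisher's conservatism. At 50% positive the z test gives 44.7%, so 8.5 of the 27.8 points (64.0 − 36.2) come from the choice of test.

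Titres are not thrown away, since every value is listed. This too stands, and it makes the remedy cheap, but a by-subject listing compares no arms. SAP 5 gives default statistics for continuous variables, and the appendices allow tables to be reorganised in programming. Neither commits to a titre summary, and the specific instruction in 8.4 is a count and percentage.

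A titre comparison would not be a clean randomised one. The per-protocol set depends on post-randomisation outcome, and subjects discharged early may have no later sample. This stands and limits how any such estimate should be read. It affects the Yes/No table equally.

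A reader might infer three stronger points that the documents do not support:

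- **That most of the power is always lost.** Under these assumptions that holds only when response is near-saturated or rare, and no document gives the responder share.
- **That the objective exists to detect harm to the antibody response.** The Protocol describes cytokine inhibition, but neither document states such a question, and the SAP places IgM among exploratory efficacy endpoints.
- **That 50% against 25% is the plan's contrast for IgM.** The Protocol gives it for treatment failure.

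**Conclusion.** The point holds as a low-cost improvement to an exploratory analysis. The only planned summary by arm is a cumulative Yes/No with an undefined cut, while the titre behind it is collected and left unsummarised. A moderate difference in titre among responders could not appear.

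The size depends on a responder share the documents do not give. The information lost is about 36% at best (a median cut), about half near an 80% share, and 78% at 95%. The cumulative rule moves the table toward the costly end. All of this rests on a normal log titre, and the powers also on a 0.5 SD shift with full samples in 44 per arm; the 76% figure further assumes a Day 1 correlation of 0.5 and no censoring. The primary analysis is unaffected. The available SAP text ends within the listing layouts, so a response definition later in that appendix cannot be excluded. It would settle the cut but not the missing titre summary.

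**What to change.** In SAP 8.4 and Table 14.2.3.1:

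1. Add, by arm, the number with a sample and the geometric mean titre on the scheduled serum days (1, 7 and 14), and show all three days in Listing 16.2.6.5.
2. Add a descriptive ratio of each dose to placebo with a 95% CI, adjusted for Day 1 log titre.
3. State the rule for values below the assay limit, for example half the limit, and report how many values it affects.
4. Keep Yes/No as a secondary row. State the cut and whether a Day 1 positive counts as a response.
5. Label the block exploratory, and note that the per-protocol set and early discharge limit who has a post-baseline sample.

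While the table is open, correct its layout. Both active columns are headed 120 mg, the source cited is the nasal oxygen listing (16.2.6.3) instead of 16.2.6.5, and the Day 2 to 4 rows do not match the serum days in SAP Table 1.

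The cost is one table block and a few sentences, settled before unblinding. It needs no new samples and spends no alpha.

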9. SAFETY ANALYSES

All safety analyses will be based on the Safety Population.

9.1. Adverse Events

An adverse event (AE) is defined as any unfavorable and unintended change in the structure, function, or chemistry of the body, or worsening of a pre-existing condition, temporally associated with the use of a product whether or not considered related to the use of the product. In this study, such changes will be monitored, classified, and summarized, as Clinical or Laboratory AEs. Medical conditions/diseases present before starting the investigational drug will be considered adverse events only if they worsen after starting study treatment. Verbatim terms on CRFs will be mapped to preferred terms (PTs) and system organ classes (SOCs) using the Medical Dictionary for Regulatory Activities (MedDRA) (version 23.0).

9.1.1. Severity

AEs are graded by the investigator as Grade 1 (mild), Grade 2 (moderate), Grade 3 (severe), Grade 4 (potentially life threatening) or Grade 5 (death) according to the NCI Common Terminology Criteria for Adverse Events version 5.0.

9.1.2. Relationship

Based on the criteria described below, AEs will be classified according to one of the following categories:

- Related the investigator considers that there is a causal relationship between the event and study drug
- Probably related the investigator considers that there is a probability of a causal relationship of the event to the study drug
- Possibly related the investigator considers that there is a possible causal relationship of the event to the study drug
- Unlikely related the investigator considers that there is an unlikely causal relationship of the event to the study drug
- Not related the investigator considers that the event has no relationship to administration of the study drug

For the purpose of analysis, related AEs are those reported as "Related," "Probably related," "Possibly related" and unrelated AEs are those reported as "Unlikely related" or "Not related." Events for which the investigator did not record relationship will be considered related for analysis. Data listings will show relationship as missing.

9.1.3. Serious Adverse Events

An SAE is any AE that meets one of the following conditions:

CONFIDENTIAL Page 13 03DEC2021

- Is immediately life-threatening (e.g., participant was, in the view of the Investigator, at immediate risk of death from the event as it occurred);
- Requires or prolongs hospitalization;
- Results in congenital anomaly or birth defect;
- Results in persistent or significant disability/incapacity;
- Is an important medical event that may not result in death or be life threatening, but based upon appropriate medical judgment, may jeopardize the participant and may require medical or surgical intervention to prevent one of the outcomes listed above;
- Results in death.

9.1.4. Treatment-Emergent Adverse Events (TEAEs)

9.1.4.1. Definition of Treatment-Emergent

TEAEs include the following:

- a) Post-treatment complications that occur as a result of protocol mandated procedure.
- b) Any pre-existing condition that increases in severity, or changes in nature during or as a consequence of the study drug phase of a human clinical trial, will also be considered an AE.
- c) Complications and termination of pregnancy; see protocol v5.0 section 7.1.7 for additional information.
- d) Non-elective medical or surgical procedures.

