6.2.3 Safety Assessments

6.2.3.1 SARS-CoV-2 associated events

The medical record will be reviewed daily for the occurrence of SARS-CoV-2 associated events, which include shortness of breath and arterial thrombosis (myocardial infarction, stroke, peripheral blood clot).

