7. EVALUATION OF SAFTY AND MANAGEMENT OF TOXICITY

7.1 Safety Parameters

7.1.1 Adverse Events (AEs)

An AE (also referred to as an adverse experience) is defined as any unfavorable and unintended sign, symptom, or laboratory abnormality that is temporarily associated with the use of a drug or treatment and does not imply any judgement about causality. An adverse event can arise with any use of a drug or treatment regardless of route of administration, dose, and may be delayed after a drug or treatment has been discontinued. An adverse event is not the same as an "overdose"; an overdose is a doserelated event specifically caused by exposure to an increased amount of drug. An unexpected AE is:

- Not identified in the Investigator's Brochure (IB) or otherwise not expected from the characteristics of the clinical material
- Not listed at the specificity or severity that has been previously observed
- Not specifically mentioned in the IB as known to occur with the particular drug under investigation, even though the adverse event may be known to occur with other drugs in the same pharmacologic class or with drugs that share pharmacologic properties with the study drug.

Treatment emergent AEs (TEAE) include the following:

• Post-treatment complications that occur as a result of protocol mandated procedure

- Any pre-existing condition that increases in severity, or changes in nature during or as a consequence of the study drug phase of a human clinical trial, will also be considered an AE
- Complications and termination of pregnancy; see Section 7.1.8 for additional information.
- Non-elective medical or surgical procedures

Study related AEs do not include the following:

- Expected complications or clinical consequences due to elective medical or surgical procedures
- Pre-existing diseases or conditions or laboratory abnormalities present or detected before study enrollment or prior to the first administration of study drug that do not worsen
- Overdose of non-study drug
- Incorrect or increased dose administration of study drug without adverse clinical sequelae
- Any laboratory abnormality that is considered as non-significant
- Uncomplicated pregnancy
- An induced elective abortion to terminate a pregnancy without medical reason

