7.1.2 Serious Adverse Events (SAEs)

A SAE is any AE that meets one of the following conditions:

- Is immediately life-threatening (e.g., participant was, in the view of the Investigator, at immediate risk of death from the event as it occurred).
- Requires or prolongs hospitalization;
- Results in congenital anomaly or birth defect;
- Results in persistent or significant disability/incapacity;
- Is an important medical event that may not result in death or be life threatening, but based upon appropriate medical judgment, may jeopardize the participant and may require medical or surgical intervention to prevent one of the outcomes listed above.
- Results in death

Important medical events that do not result in death, are life-threatening, or require hospitalization may be considered as an SAE when, in the judgement of the Investigator, potentially jeopardize the study participant and may require medical or surgical intervention.

SAE's occurring up to and including the final study visit will be collected regardless of the Investigator's opinion of causation.

If an Investigator becomes aware of an SAE that has occurred after a participant has completed the study, the Investigator should report the SAE to the sponsor regardless of the Investigator's opinion of causation.

SAEs should be followed until resolution. The reporting period for SAEs is described in Section 9.6.2.

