2. STUDY OBJECTIVES

2.1. Primary Objectives

The primary objectives of the study are to evaluate the following:

- Incidence of serious adverse events relative to treatment group
- Incidence of treatment failure within 28 days from enrollment

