9.1.5. Summaries of Adverse Events

An overall summary of AEs will display, by treatment, the number and percentage of subjects who had any TEAE, whose strongest TEAE relationship to study drug is related or not related, whose maximum TEAE severity is mild, moderate, or severe, who had any SAE, any Serious TEAE, any TEAE leading to study discontinuation, and any TEAE leading to death.

The following summaries (number and percentage of subjects) of AEs (by SOC and PT) will be provided by treatment:

- All TEAEs
- All TEAEs by strongest relationship
- All TEAEs by maximum severity grade
- All Related TEAEs by maximum severity grade

CONFIDENTIAL Page 14 03DEC2021

- All Serious AEs
- All Serious TEAEs
- All TEAEs leading to study discontinuation
- All TEAEs leading to death

These summaries will present the number and percentage of subjects with at least one qualifying AE. Subjects may have more than one AE per SOC and PT. Each summary will be ordered by descending order of incidence of SOC and PT within each SOC.

In addition to the by-treatment summaries, data listings will be provided for the following:

- All AEs (with a flag indicating whether the event is treatment emergent)
- SAEs
- AEs leading to study discontinuation
- Deaths

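### The headline SAE percentage, the first-listed primary objective, includes COVID-19 progression, and no planned row separates it from other serious harm

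*SAP*

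**What the plan says.** Protocol 2.2 and SAP 2.1 list "Incidence of serious adverse events relative to treatment group" first among the primary objectives, ahead of treatment failure.

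The definitions decide what enters that count:

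- **Worsening is an adverse event.** Protocol 6.2.2 has worsening of an existing illness after the first dose recorded as an AE. SAP 9.1 says that conditions present before dosing "will be considered adverse events only if they worsen after starting study treatment". SAP 9.1.4.1 makes treatment-emergent "Any pre-existing condition that increases in severity, or changes in nature during or as a consequence of the study drug phase".
- **The exclusion is narrow.** Among pre-existing findings, Protocol 7.1.1 leaves out diseases, conditions or "laboratory abnormalities present or detected before study enrollment or prior to the first administration of study drug that do not worsen".
- **Seriousness.** Under Protocol 7.1.2 and SAP 9.1.3 an AE is serious if, among other criteria, it is fatal, is immediately life-threatening, or "Requires or prolongs hospitalization".
- **Cause is not a filter.** Protocol 7.1.2 says that SAEs "occurring up to and including the final study visit will be collected regardless of the" investigator's opinion of causation.

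For output, SAP 9.1.5 plans an overall summary of subjects "who had any SAE, any Serious TEAE, any TEAE leading to study discontinuation, and any TEAE leading to death" (Table 14.3.1.1). It also plans SAEs and serious TEAEs by system organ class and preferred term (Tables 14.3.2.1 and 14.3.2.2), related TEAEs by grade, and listings. No test or margin is set for SAEs.

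**The concern.** Every participant enters with COVID-19. Intubation, ECMO or death from it is a worsening of a pre-existing illness and meets at least one seriousness criterion, so the definitions make it an SAE. The same events are the WHO level 6 or greater component of treatment failure (Protocol 8.6, SAP 8.1). Neither document exempts endpoint events or disease progression from SAE counting.

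The any-SAE line of Table 14.3.1.1 and the at-least-one rows at the top of Tables 14.3.2.1 and 14.3.2.2 therefore combine progression with everything else. If the drug reduces progression, that benefit offsets any excess of other serious harm in these rows. If it does not, the excess is diluted by a large common background. Protocol 7.3.2 names serious harms that it watches for apart from progression, such as opportunistic infection, gastric hemorrhage and malignant hypertension. The headline figure for the safety objective is where a reader would first look for an imbalance in them.

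**Working it through.** **Inputs**

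- Group size: 44 per arm (Protocol 8.2, SAP 4).
- Progression on placebo, *p*: 50%. Protocol 8.2 gives this for progression to WHO level 6 or greater. SAP 4 attaches the same 50% to the whole treatment-failure composite.
- Progression on drug: 25%. Protocol 8.2 gives 25% as the target for treatment failure; for progression alone it is an assumption.
- Other SAEs on placebo, *q*: the documents give no rate. Assumed 5% to 20%, doubled on drug, independent of progression.

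**The plan's own figure.** None exists for SAEs. The stated 70% exit probability concerns treatment failure. A two-look O'Brien-Fleming-type boundary at information 0.5 and 1, with an unpooled z statistic (drift 0.25 / √((0.25 + 0.1875)/44) = 2.507), gives 70.4%. That reproduces the figure but says nothing about SAEs.

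**Formula.** Any-SAE rate = 1 − (1 − progression)(1 − other). For *q* = 10%: placebo 1 − 0.50 × 0.90 = 55%; drug 1 − 0.75 × 0.80 = 40%.

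The last three columns come from exact binomial and two-sided Fisher enumeration at 44 v 44. The separate row counts only SAEs other than progression.

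| Other SAEs, placebo → drug | Any SAE, placebo v drug | Chance drug arm shows more: any-SAE row | Chance drug arm shows more: separate row | Fisher power, separate row |
|---|---|---|---|---|
| 5% → 10% | 52.5% v 32.5% | 2% | 76% | 5% |
| 10% → 20% | 55% v 40% | 6% | 88% | 17% |
| 15% → 30% | 57.5% v 47.5% | 15% | 94% | 29% |
| 20% → 40% | 60% v 55% | 28% | 98% | 45% |

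In the any-SAE row the chance of a significant excess on drug is below 0.4% in all four cases.

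**When the reversal occurs.** With progression *p* v *p*/2 and other SAEs *q* v 2*q*:

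- drug: 1 − (1 − *p*/2)(1 − 2*q*) = *p*/2 + 2*q* − *pq*
- placebo: 1 − (1 − *p*)(1 − *q*) = *p* + *q* − *pq*
- difference, drug minus placebo: *q* − *p*/2

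The drug looks safer only if *q* is below *p*/2, that is, below 25% when *p* is 50%. The same condition holds if the two event types are disjoint instead of independent.

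**Lower progression rates**

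- 30% v 15%, other 10% → 20%: 37% v 32%, still reversed.
- 20% v 10%, other 10% → 20%: 28% v 28%, break-even.
- 20% v 10%, other 15% → 30%: 32% v 37%, the excess shows.
- 10% v 5%, other 10% → 20%: 19% v 24%, the excess shows.

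**No efficacy.** Progression 50% v 50%, other 10% → 20%: 1 − 0.50 × 0.90 = 55% v 1 − 0.50 × 0.80 = 60%. A doubling reads as 0.60/0.55 = 1.09.

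**The case against.** A reader might infer that the safety analysis as a whole would hide a doubling of serious harm. The documents do not support that. Only the any-SAE line and the at-least-one rows pool. Tables 14.3.2.1 and 14.3.2.2 are by arm and preferred term, so a gastric hemorrhage or an infection has its own row, and Listing 16.2.7.2 gives relationship and seriousness criterion for each event. With 44 per arm these can be read closely. This stands, and it limits the point to the headline. It does not supply the aggregate: one subject can appear under several terms, so term rows cannot be added up to subjects with any SAE other than progression. That count would have to be built from listings without a prespecified term list. Nor does any table give serious related events. Related TEAEs are tabulated by grade, and that layout stops at Grade 4 although Grade 5 is death.

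A reader might also infer that the two primary objectives measure the same events. They overlap only in the clinical-progression part. Consent withdrawal, hospital transfer and drug discontinuation are failures but not in themselves SAEs, and SAE collection runs past Day 28.

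It can be said, too, that sites may not report progression as an SAE. Protocol 6.2.3.1 states that "The medical record will be reviewed daily for the occurrence of SARS-CoV-2 associated events", under a heading separate from adverse events, and Protocol 6.1.3 lists complications, including death, apart from adverse effects. This is not an exemption, but the documents do not say how sites will report. The inclusion follows from the definitions, not from an explicit instruction.

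Finally, the SAE comparison is descriptive and the trial is small, so no formal conclusion is at risk. That is fair, and it keeps the point modest.

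**Conclusion.** The concern holds for the headline SAE figure. By the documents' definitions, progression to WHO level 6 to 8 is both an SAE and a treatment failure, so the any-SAE percentage cannot be read apart from efficacy. At 50% v 25% progression, a doubling of other SAEs from an assumed 5% to 20% would appear as an advantage for the drug of 20 down to 5 percentage points.

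This rests on an assumed background SAE rate, on 25% as the progression rate on drug, and on sites reporting progression as the definitions require. With progression halved, the reversal disappears once the background rate reaches half the placebo progression rate. The by-term tables and listings remain informative, so the gap is one missing aggregate and one missing serious-related display. It is worth closing because it bears on a primary objective and the remedy is cheap.

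**What to change.** In SAP 9.1.5 and Tables 14.3.1.1, 14.3.2.1 and 14.3.2.2:

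1. Keep the all-SAE row as the headline, and state that WHO level 6 or greater and COVID-19 death events are included in it.
2. Beside it, add by-arm incidence of SAEs excluding those events, from a term list frozen before unblinding, with confidence intervals.
3. Add a row for serious related TEAEs.

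Read the rows together. The row without progression should not replace the all-SAE row, because drug harm such as an infection may be coded under respiratory failure or a similar term and would then drop out of view.

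The cost is SAP wording, extra table rows and a blinded medical review of the term list; the data are already collected. The new row makes a signal visible but does not give power: at 10% v 20% the expected counts are 4.4 v 8.8 of 44, with about 17% Fisher power.
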